ASA challenge is conducted during the second visit if needed, according to modified international protocol (15-16). FEV1 should be at least 1.5 L and > 60% of predicted before challenge or desensitization. Patient will receive 25 mg ASA at a hospital setting. If no remarkable symptoms are seen, patient will receive 1-2 hours later another 25 mg ASA at a hospital setting.

ASA challenge positive result:

1. Naso-ocular alone: a 30 % or > increase in at least one of the following VAS (0-10 cm) scores: nasal obstruction, nasal discharge, postnasal drip, eye itching. These may exist with or without objective signs of increased nasal turbinate swelling/discharge or eye redness in examination.
2. Naso-ocular (please see 1.) and a 15% or > decline in FEV1 or in PEF (Classic reaction)
3. Lower respiratory reaction only (FEV1 or PEF declines by >20%)
4. Laryngospasm with or without 1-3 (flat or notched inspiratory curve)
5. Systemic reaction: hives, flush, gastric pain, hypotension

Patients Randomization and the treatment arms I-II occurs after 1st (or 2nd for ASA challenged) visit. The patients are randomized to two treatment arms: I) subcutaneous injections of placebo once per month for 16 weeks II) subcutaneous injections of Mepolizumab once per month for 16 weeks. Mepolizumab 100 mg / Placebo (NaCl solution)

is injected subcutaneously once per month, for a total of 16 weeks. GSK provides the randomization codes to each center.

Table1 the study protocol

| Time | -4 weeks | -2 weeks | 0 weeks | 4 weeks | 8 weeks | 12 weeks | 16 weeks | 20 weeks |
|--|---------------|----------------------|----------------|----------------|----------------|----------------|-----------------|--------------|
| Visit | 1 | 2 | 3 | 4 | 5 | 6 | 7 | 8 |
| | Rekrytointi | ASA-aslustus | 1. pistoskerta | 2. pistoskerta | 3. pistoskerta | 4. pistoskerta | Seurantakäynti | Loppukäynti |
| Name of the visit | Recruitment | ASA-challenge | 1st injection | 2nd injection | 3rd injection | 4th injection | Follow-up visit | End of Trial |
| Informed Consent | x | | | | | | | |
| Review Inclusion / Exclusion Criteria | x | x No flu 2 we before | x | | | | | |
| Medical History comorbidities | x | | | | | | | |
| Randomization | x | x | | | | | | |
| Visiting Doctor | x | x | x | x | x | x | x | x |
| Visiting Nurse | x | x | x | x | x | x | x | x |
| Review of Concomitant Medication | x | x | x | x | x | x | x | x |

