| Visits, hospitalisations, exacerbations, sick leave, productivity | Previous year | | | | | | | |
| Allergy test = serum specific IgE test (pölyerittely) | x | | | | | | | |
| | x | | | | | | x | |
| ASA challenge test (to subjects without previous challenge-test-confirmed NERD dg) | | x | | | | | | |
| Treatment with IMP | | | x | x | x | x | | |
| Check side-effects | | x | x | x | x | x | x | x |
| ENT visit (+ lung examination) | x | x | x | x | x | x | x | x |
| Check CRS control | x | x | x | x | x | x | x | x |
| Pulmonologist visit | x | | | | | | x | |
| Check asthma control | x | x | x | x | x | x | x | x |
| Questionnaire-packet: SNOT-22, 15D, AQLQ, Asthma control | x | x | x | x | x | x | x | x |

| | | | | | | | | |
|---|---|----|---|---|---|---|---|-------------------|
| test, 2xNetherlands-Q | | | | | | | | |
| VAS symptoms | | x | | | | | | |
| Baseline characters questionnaire (esitietokaavake) | x | | | | | | | (x) if changed |
| Acoustic rhinometry (ARM) | x | xx | x | x | x | x | x | x |
| nNO | x | xx | | | | | x | |
| eNO | x | | | | | | x | |
| Olfaction Sniffin' sticks | x | | x | x | x | x | x | x |
| sinus CT scans | x | | | | | | | |
| Blood analysis for Biobank | x | | | - | - | - | | - |
| Blood samples (5 EDTA tubes) for metabolomics & genomics | x | xx | x | x | x | x | x | x |
| Urine samples for metabolomics | x | xx | x | x | x | x | x | x |
| Fecal sample for microbiome | x | | x | x | x | x | x | x |
| Nasal samples (microbiome, transcriptomics, histology) | x | xx | | | | | x | |
| Spirometry | x | | | | | | x | |
| PEF 1 week | x | x | | | | | x | |
| microspirometry | | x | | | | | | |
| PEF at visit | x | x | x | x | x | x | x | x |
| PNIF at visit | x | x | x | x | x | x | x | x |
| Check disease relapse | x | x | x | x | x | x | x | x |
| Consider additional therapy /referral to operation | x | x | x | x | x | x | x | x |

Study endpoints

Primary, Change from baseline

endoscopic nasal polyp score (total score ranges between 0-8 of both sides), SNOT22 symptom score, VAS score (of smell loss, obstruction, postnasal drip, nasal discharge, facial pain/pressure) and, exacerbation-rate. Exacerbation means that patient has at least one of the following due to airway symptoms: oral corticosteroid course; antibiotic courses; sinus lavation; hospitalization.

Secondary, Change from baseline

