· Details of all pregnancies in female participants will be collected after the start of study intervention and until 16 weeks after the last dose.

· If a pregnancy is reported, the investigator will record pregnancy information on the appropriate form and submit it to GSK within 24 hours of learning of the pregnancy. While pregnancy itself is not considered to be an AE or SAE, any pregnancy complication or elective termination of a pregnancy for medical reasons will be reported as an AE or SAE.

· Abnormal pregnancy outcomes (e.g., spontaneous abortion, fetal death, stillbirth, congenital anomalies, ectopic pregnancy) are considered SAEs and will be reported as such.

- The participant will be followed to determine the outcome of the pregnancy. The investigator will collect follow-up information on the participant and the neonate, and the information will be forwarded to the sponsor.
- Any female participant who becomes pregnant while participating in the study will discontinue study intervention.

SAE and pregnancy reporting:

Sponsor will promptly notify GlaxoSmithKline of all SAEs and pregnancies (if applicable) that have occurred for participants enrolled in this Study Drug Appendix, in accordance with the timelines and procedures specified in the Protocol/appendix. In addition, the sponsor will reasonably obtain and provide follow-up information as available, to GSK upon request.

Follow-up of the patient after the study

There is no follow-up after the study in the research protocol. However, the follow-up monitoring is performed according to normal clinical routine, as the recruited patients are under continuous monitoring and treatment by HUS, KYS and TAYS, in which the study centers are also located.

Patients who are discontinuing their participation are asked the permission to use the data collected.

Data management

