The statistical analyses will be conducted in the modified intention-to-treat (mITT) population, defined as all randomized participants who received at least one dose of the investigational medicinal product and fulfilled the inclusion criteria. One randomized participant was excluded due to failure to meet inclusion criteria, resulting in 47 participants per treatment group. All analyses were performed blinded to treatment allocation, and the randomization code was opened only after the trial was closed and the primary analyses completed. The sample size was calculated to provide 80% power to detect clinically meaningful differences in the coprimary endpoints using a two-sided significance level of 0.05. Baseline was defined as the recruitment visit, occurring approximately eight weeks prior to initiation of the investigational medicinal product. Participants received four injections over a 16-week treatment period, followed by an additional eight-week observation period without treatment, after which final measurements were obtained. Continuous variables are summarized using means with standard deviations or medians with interquartile ranges, as appropriate, and categorical variables using frequencies and percentages. The coprimary endpoints and all secondary continuous outcomes were analyzed as changes from baseline using linear mixed-effects models. These models included fixed effects for treatment group, time, and their interaction, and a random intercept for participants to account for within-subject correlation over repeated measurements. Group-specific changes from baseline were estimated at each follow-up time point, and treatment effects were assessed by comparing differences in these estimated changes between groups. Results are reported as mean differences with 95% confidence intervals. A two-sided significance level of $p < 0.05$ was applied to all analyses, and no formal adjustment for multiple comparisons was performed. Model assumptions were evaluated by visual inspection of residual plots to assess normality and homoscedasticity, and by examination of fitted values and influence diagnostics to identify outliers or model instability. The linear mixed-effects modeling framework was selected because it accommodates unequally spaced measurements and missing observations and provides unbiased estimates under the missing-at-random assumption.

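### Pregnancies are to be collected until 16 weeks after the last dose, but planned study contact ends 8 weeks after it and the protocol disclaims later study follow-up

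*Protocol*

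**What the plan says.** **Collection window.** Protocol, Pregnancy: "Details of all pregnancies in female participants will be collected after the start of study intervention and until 16 weeks after the last dose". The same section says of a pregnancy that has been reported: "The participant will be followed to determine the outcome of the pregnancy". It also asks for information on the neonate, classes abnormal outcomes as serious adverse events, and gives the investigator 24 hours from becoming aware of a pregnancy to submit the form to the manufacturer.

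**Visit schedule.** In Table 1 the last three columns are timed "12 weeks | 16 weeks | 20 weeks" and named "4th injection | Follow-up visit | End of Trial". The study drug row reads "Treatment with IMP | | | x | x | x | x", which marks visits 3 to 6 only. Table 2 gives the same weeks for these visits.

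**After the last visit.** Protocol, Follow-up of the patient after the study: "There is no follow-up after the study in the research protocol". The next sentence continues: "However, the follow-up monitoring is performed according to normal clinical routine, as the recruited patients are under continuous monitoring and treatment by HUS, KYS and". A third hospital completes that list, and the section notes that the study centers are in these hospitals.

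**SAP timeline.** "Participants received four injections over a 16-week treatment period, followed by an additional eight-week observation period without treatment, after which final measurements were obtained".

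**The concern.** The protocol undertakes to collect every pregnancy in a period that runs past its last visit, and then says that it has no follow-up after the study. Nothing in the visible text assigns a visit, a call or an enquiry to the weeks in between.

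The stake is completeness of the safety data. Females of reproductive potential may be enrolled, abnormal pregnancy outcomes count as serious adverse events, and the sponsor must notify the manufacturer of all pregnancies. If nobody is asked after week 20, a report of no pregnancies between weeks 20 and 28 cannot separate none occurring from none being sought. The trial could not then show that it met its own window.

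**Working it through.** This is calendar arithmetic on the schedule. The plan states no coverage figure to reproduce, and no power or error rate enters.

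**Inputs**
- Last dose: week 12 (Table 1, visit 6; no study drug at visits 7 and 8).
- Last planned contact: week 20 (Tables 1 and 2, visit 8). The two tables time the pre-treatment visits differently, but they agree from week 0 onward.
- Window: from the start of study intervention (week 0) to 16 weeks after the last dose (Pregnancy section).
- SAP final measurement: week 24, if its 16 weeks of treatment and 8 weeks of observation are simply added.

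**Formulas**
- End of window = last dose + 16 = 12 + 16 = week 28.
- Weeks without planned contact = end of window − last planned contact.
- Share of the post-dose period = gap / 16. Share of the full window = gap / 28.

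| Reading | Last contact | Weeks after last dose | Gap | Share of 16 post-dose weeks | Share of 28-week window |
|---|---|---|---|---|---|
| Protocol Tables 1 and 2 | week 20 | 20 − 12 = 8 | 28 − 20 = 8 weeks | 8/16 = 50% | 8/28 = 28.6% |
| SAP, literal 16 + 8 | week 24 | 24 − 12 = 12 | 28 − 24 = 4 weeks | 4/16 = 25% | 4/28 = 14.3% |

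If the SAP's eight weeks are instead counted from the last injection, its final visit falls at 12 + 8 = week 20 and the gap is again 8 weeks. None of these readings closes the gap.

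**A second conflict, which does not depend on the week count.** A conception during treatment has to be followed to its outcome, and for a pregnancy carried to term that lies well past week 20. The follow-up section makes no exception for this. Its sentence therefore conflicts with the Pregnancy section even if the 16-week window were shortened.

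**The case against.** The best answer is that the duty is triggered by a report. The form and the 24-hour limit apply once a pregnancy is known, and a window for accepting reports does not logically require a visit on its last day. On that view the follow-up section means only that there are no more scheduled visits. Patients also remain in care at the hospitals that house the study centers, and the protocol records contacts between patient and study unit in the eCRF. Finally, the protocol refers to a study drug appendix that is not in the text reviewed, and the consent pages were not available. Either could tell participants to report a pregnancy.

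Part of this stands. A reader might infer that no follow-up of any kind exists after week 20. The documents do not support that, because routine monitoring continues. A reader might also infer that half of the collection window is uncovered. That holds only for the 16 weeks after the last dose. The window opens at the first dose, so the share is about 29%. Nor can it be said that pregnancies were or will be missed, since the documents give no number of women of reproductive potential and no expected number of pregnancies.

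The rest does not close the gap. The Pregnancy section promises details of all pregnancies, not only those that happen to be reported. The follow-up section places routine care outside the research protocol and gives it no interval, no pregnancy enquiry and no path to the form. The eCRF sentence records contacts but schedules none. An unseen appendix might supply a procedure, but it would not remove the conflict in the protocol's own wording.

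**Conclusion.** The point holds as an internal inconsistency in safety collection. On the protocol's tables, the last 8 of the 16 post-dose weeks (8 of 28 weeks, about 29%, of the full window) have no planned study contact. On the SAP's literal timeline the figure is 4 weeks. These weeks depend on routine care, with no stated route to the pregnancy form. Separately, the follow-up sentence conflicts with following known pregnancies to their outcome.

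This rests on the last dose being given at week 12 as scheduled, and on the visible text, which may omit an appendix or consent wording. The efficacy analyses are untouched. The effect on the count of pregnancies is unknown and could be nil. The correction is worth making because it is cheap and because the protocol treats abnormal pregnancy outcomes as serious adverse events.

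**What to change.** Reconcile the Pregnancy section, the follow-up section and Table 1 so that the stated collection window and the last planned study contact agree. Which passage changes is for the sponsor to decide.

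- If the window is kept, add one remote contact at its end to Table 1, and exempt pregnancy collection from the follow-up section's sentence.
- Whichever window is chosen, exempt outcome follow-up of a known pregnancy from that sentence.
- State which week the final visit falls in, so that the SAP and Table 1 give the same gap.
- The SAP speaks of the trial as closed. If visits have ended, the safety report should state up to which week pregnancies were actually sought, and by what means.

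The cost is a wording change and, if the window is kept, one remote contact for the participants concerned. For a completed trial it is a sentence or two in the report.

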The statistical analyses will be conducted in the modified intention-to-treat (mITT) population, defined as all randomized participants who received at least one dose of the investigational medicinal product and fulfilled the inclusion criteria. One randomized participant was excluded due to failure to meet inclusion criteria, resulting in 47 participants per treatment group. All analyses were performed blinded to treatment allocation, and the randomization code was opened only after the trial was closed and the primary analyses completed. The sample size was calculated to provide 80% power to detect clinically meaningful differences in the coprimary endpoints using a two-sided significance level of 0.05. Baseline was defined as the recruitment visit, occurring approximately eight weeks prior to initiation of the investigational medicinal product. Participants received four injections over a 16-week treatment period, followed by an additional eight-week observation period without treatment, after which final measurements were obtained. Continuous variables are summarized using means with standard deviations or medians with interquartile ranges, as appropriate, and categorical variables using frequencies and percentages. The coprimary endpoints and all secondary continuous outcomes were analyzed as changes from baseline using linear mixed-effects models. These models included fixed effects for treatment group, time, and their interaction, and a random intercept for participants to account for within-subject correlation over repeated measurements. Group-specific changes from baseline were estimated at each follow-up time point, and treatment effects were assessed by comparing differences in these estimated changes between groups. Results are reported as mean differences with 95% confidence intervals. A two-sided significance level of $p < 0.05$ was applied to all analyses, and no formal adjustment for multiple comparisons was performed. Model assumptions were evaluated by visual inspection of residual plots to assess normality and homoscedasticity, and by examination of fitted values and influence diagnostics to identify outliers or model instability. The linear mixed-effects modeling framework was selected because it accommodates unequally spaced measurements and missing observations and provides unbiased estimates under the missing-at-random assumption.

No imputation methods were applied for missing data. To assess the robustness of the findings and the plausibility of the missing-at-random assumption, sensitivity analyses were performed. These included a complete-case analysis restricted to participants with available data at all time points and an analysis excluding participants who received systemic oral corticosteroids

for exacerbations at any point during the trial. The corticosteroid exclusion analysis evaluated the coprimary outcomes (Nasal Polyp Score and SNOT-22 total score) as well as lung function outcomes, including relative changes in peak nasal inspiratory flow, peak expiratory flow, forced expiratory volume in one second, and corresponding microspirometry measures. Sensitivity analyses were conducted in the per-protocol population on an available-case basis using the same statistical models, confidence intervals, and significance thresholds as the primary analyses. Consistency of results across analyses was used to support the validity of the primary findings. All statistical analyses were performed using R statistical software, version 4.5.1.

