Other medication such as dosing-up medication, and medication of exacerbations (antibiotics, bronchodilators, nasal decongestants, systemic corticosteroids)

BEos, NPeos

signs of Type2-inflammation in blood and nasal samples

nasal and lung function test results (FEV1, peak expiratory flow rate, eNO, nNO and/or MCA in Acoustic rhinometry, PNIF, Sniffin' sticks 12)

Number of patients who met criteria for requiring surgery for polyposis at each time point

Questionnaire-packet: 15D, mini-AQLQ, Asthma control test, iMCQ, iPCQ, WPAI, EQ-5D-5L

Consideration/planning of a CRS-operation due to airway symptoms

Cost-effect and productivity (iMCQ,iPCQ questionnaires, sick leaves due to airway symptoms)

Safety (adverse effects)

The following clinical data are also collected:

Lund-Mackay score of Sinus CT scans/Cone beam CT, performed ~~12 months~~ prior to the study.

Questions concerning uncontrolled CRS according to EPOS12 and EPOS20 -criteria

The patient will know the treatment arm when the trial has been terminated. The patient can discuss with the doctor of the need to continue or start with advanced or another therapy or referral to consideration of operation, if needed. Results of the samples will be compared with the results of other studies (AirGOs-oper and AirGOs-medical).

Reporting and monitoring of adverse events and -reactions

Reporting of adverse events and -reactions is performed as follows: immediate announcement to the healthcare personnel, the patient and the principal investigator, and by recording and transferring the data to an electronic follow-up form (eCRF). The report will be forwarded to the supervisory authorities if necessary.

The subject's condition is monitored and treatment is carried out properly. eg. (medical care, treatment calls, medical appointments, if necessary), and all contacts between the study patient and the study unit are recorded in the patient records and eCRF-form and the necessary reports are submitted to the supervisory authorities if necessary.

Pharmaceutical manufacturer GlaxoSmithKleine will also receive a safety report from the research unit on the incident.

Adverse event and reaction reporting-, monitoring and registration is performed in accordance with Finnish legislation. We follow EU-standards and guidelines as well as the Declaration of Helsinki of the World Medical Assembly.

Pregnancy:

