Statistics. Data analysis will be carried out on the relationship between Mepolizumab and placebo treatment. Variables tested in the statistical models include age, gender, symptoms, exacerbations, infections, medications, endoscopic findings, sick leave, allergy, side-effects of treatment, hospitalizations, and other factors at different time-points. Student's t test (or KW, MWU tests, in case of not normally distributed sample), as well as adjusted linear regression models are used for continuous measures. A statistical analysis plan (such as correction for multiple testing) will be drawn up with advice from the statistical department at the University of Helsinki.

We will use several software: R 3.0.2, SPSS 22.0 Statistical Software Package (SPSS, Chicago, IL) and STATA (Release 13.1 software, StataCorp, Texas, USA). For comparisons, the results will be analyzed by Logistic regression, Student's t-, Chi-square, (nonparametric) Fisher's exact and Mann Whitney U test. P-values less than 0.05 are considered statistically significant. Results of logistic regression are reported as odds ratios (OR) with 95% confidence intervals. All models will be adjusted by selected covariates (potential confounding factors).

Sample handling

The samples will be stored at Helsinki Biobank or at the University of Helsinki.

Table 2. Samples and their schedule. The sample protocol is reduced in KYS and TAYS.

| Time | -8 weeks | -4 weeks | 0 weeks | 4 weeks | 8 weeks | 12 weeks | 16 weeks | 20 weeks |
|--|---------------------|---------------------------|---------------------|-------------------------|---------------------|---------------------|--|---------------------|
| Visit | 1 | 2 | 3 | 4 | 5 | 6 | 7 | 8 |
| Name of the visit | Recruitment | ASA-challenge (if needed) | 1st injection | 2nd injection | 3rd injection | 4th injection | Follow-up visit | End of Trial |
| Nasal cotton/swab samples (Microbiome, RNA) | x | xx | | | | | x | |
| Nasal biopsies under local anesthesia | X2 | x | | | | | X2 | |
| Nasopharyngeal aspirate (Microbiome) | x | | x | x | x | x | x | x |
| Fasting blood sample 18 ml ¹ | x EDTA, plasma 9 ml | xx EDTA, plasma 9+9 ml | x EDTA, plasma 9 ml | EDTA DNA 4 ml, CPT 8 ml | x EDTA, plasma 9 ml | x EDTA, plasma 9 ml | x EDTA, plasma 9 ml; EDTA DNA 4 ml, CPT 8 ml | x EDTA, plasma 9 ml |
| Biobank 0-blood sample (voluntary) | X | | | | | | | |
| Blood sample (CBC, WBC differential, S-IgE allergen profile) + ECG | X | | | | | | x | |

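### The available SAP text defines no safety population, and its one general analysis set leaves out dosed participants who failed the inclusion criteria

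*SAP*

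**What the plan says.** **SAP, first paragraph.** The text opens with "The statistical analyses will be conducted in the modified intention-to-treat (mITT) population" and does not restrict this to efficacy. Membership is then defined as "all randomized participants who received at least one dose of the investigational medicinal product and fulfilled the inclusion criteria". The SAP reports the consequence: "One randomized participant was excluded due to failure to meet inclusion criteria, resulting in 47 participants per treatment group". It names the outcomes to be modelled: "The coprimary endpoints and all secondary continuous outcomes were analyzed as changes from baseline using linear mixed-effects models". Categorical variables are to be summarised by counts and percentages.

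**SAP, second paragraph.** One other population is named: "Sensitivity analyses were conducted in the per-protocol population on an available-case basis". The available text does not define that per-protocol set. It mentions neither adverse events nor an all-dosed set, and has no rule for grouping participants by the treatment they received.

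**Protocol, Study endpoints.** The last entry in the secondary list begins "Safety (adverse effects".

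**Protocol, Data management, Statistics paragraph.** The variables to be tested include "side-effects of treatment, hospitalizations, and other factors at different time-points". No safety population is named.

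**Protocol, Table 1.** Side-effects are checked at visits 2 to 8.

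**Protocol, Reporting and monitoring of adverse events.** Recording and reporting do not depend on any analysis set: "Adverse event and reaction reporting-, monitoring and registration is performed in accordance with Finnish legislation".

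**The concern.** A safety summary describes what happened to people who were exposed. Whether an injected participant met the entry thresholds has no bearing on whether that person was exposed or harmed. An analyst who follows the SAP text and looks for a denominator for the adverse event table finds one general set, and that set carries an inclusion-criteria condition.

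An adverse event in a dosed participant who failed an inclusion criterion would then appear in neither the numerator nor the denominator of the published safety table. With 47 per arm, uncommon harms will rest on very few events. One omitted case can decide whether a table shows no events of a kind or one.

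**Working it through.** **1. What the inclusion-criteria condition does.** Let D be the randomised participants who received at least one dose, and I those who met the inclusion criteria.

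- mITT = D ∩ I.
- All-dosed safety set = D.
- Difference = D without I, that is, participants who were injected and failed an inclusion criterion.

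A participant who was never injected is outside both sets. The inclusion-criteria condition therefore removes only exposed people.

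**2. The SAP's own figure.** 47 + 47 = 94 analysed. The available text does not give the numbers randomised and dosed by arm, so 47 per group cannot be rebuilt from its inputs. One removal for failing the inclusion criteria is stated, without the arm or dosing status.

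**3. Size of the all-dosed set.**

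| Assumption about the removed participant | Safety set | Arms |
|---|---|---|
| Never dosed | 94 | 47 and 47 |
| Dosed at least once | 94 + 1 = 95 | 48 and 47 (arm unknown) |

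**4. Effect on an event rate, if that participant was dosed and had the event.** For x events among the other 47 in the arm, the change is (x + 1)/48 − x/47.

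| x | mITT rate | All-dosed rate | Change (points) |
|---|---|---|---|
| 0 | 0/47 = 0% | 1/48 = 2.1% | 2.1 |
| 1 | 1/47 = 2.1% | 2/48 = 4.2% | 2.0 |
| 2 | 2/47 = 4.3% | 3/48 = 6.3% | 2.0 |
| 5 | 5/47 = 10.6% | 6/48 = 12.5% | 1.9 |

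**5. Exact (Clopper-Pearson) 95% intervals for x = 0.**

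- 0/47: upper limit = 1 − 0.025^(1/47) = 0.0755, so 0 to 7.5%.
- 1/48: lower limit = 1 − 0.975^(1/48) = 0.0005; upper limit = 97.5% quantile of Beta(2, 47) = 0.1107. The interval is 0.05% to 11.1%.
- Difference in upper limits: 0.1107 − 0.0755 = 0.035, or 3.5 points.

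The values of x are illustrations. The documents give no adverse event counts.

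**The case against.** **The SAP does not say that safety is analysed in the mITT set.** Every outcome it names is an efficacy or function measure, and it is silent on adverse events. This stands. A reader might infer that the SAP deliberately places safety in this set, but that is an inference from an unqualified opening sentence combined with the protocol's endpoint list. It is also inexact to say that all analyses use the set, because the sensitivity analyses use the per-protocol population. The opening part of the SAP was not available, so the absence of a safety set is claimed only for the text seen.

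**The removed participant may never have been injected.** This also stands. Protocol section 2.1 places randomisation 2 to 4 weeks before trial medication, and Table 1 reviews the entry criteria again at visit 3, the day of the first injection. Someone could be randomised, found ineligible and sent home undosed.

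**No conclusion is shown to change.** Correct. The numerical example needs the participant to have been dosed and to have had the only such event in the arm. The two intervals overlap heavily, and the documents set no safety hypothesis or threshold.

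**Ineligible participants are not shown to be at higher risk.** A reader might argue that they are. The mITT definition refers to the inclusion criteria, which are mostly measures of disease type and severity. The conditions that most obviously bear on risk, such as immunosuppression, active cancer and hypersensitivity to the drug, are exclusion criteria, which the definition does not mention.

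**Harms are still recorded and reported.** Adverse events go into the eCRF, and serious ones are notified to the manufacturer, whatever the analysis set. The possible gap is confined to the summarised results.

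These points limit the size and wording of the concern. They do not supply a safety population.

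**Conclusion.** The point holds in a limited form. Either the safety summary falls by default into a set that excludes some exposed participants, or its population is undefined in the available text. The same change resolves both.

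The effect is at most one participant, on the single inclusion-criteria removal that the SAP reports. If that person was dosed, one arm goes from 47 to 48. Its rate for a given event then rises by about 2 percentage points if that person had the event. If no dose was given, the effect is nil.

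A reader might conclude that harms data have been lost. The documents do not support that, because they state neither the dosing status nor any event for the removed participant. What they support is that the one general set is unsuitable for safety and that the reader cannot tell whether it mattered.

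**What to change.** Make three changes to the SAP's first paragraph:

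1. Limit the mITT sentence to efficacy outcomes.
2. Add a safety set, for example: *Safety outcomes are analysed in all participants who received at least one injection of mepolizumab or placebo, whether or not they met the inclusion criteria, grouped by the treatment received.*
3. State whether the participant removed for failing the inclusion criteria was dosed. If so, include that participant and any events in the safety results.

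The cost is a few sentences and a separate denominator for the safety table. The protocol already has adverse events recorded in the eCRF, so no new data are needed. The safety and efficacy denominators may differ by one, which a footnote can explain. Grouping by treatment received is the usual convention; nothing in the documents suggests that anyone received the wrong product.
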